7.1 Primary endpoint - EFS

The primary endpoint is EFS as per the International Working Group (IWG) for AML [[Cheson et al., 2003](#), [ELN 2017](#)] criteria per investigator assessment. EFS is defined as the time from the date of randomization to failure to obtain a CR or CRi with adequate blood count recovery in induction (i.e. induction failure), relapse from CR or CRi with adequate blood count recovery, or death due to any cause, whichever occurs first.

7.2 Statistical hypothesis, model, and method of analysis

The study is designed to test the following statistical hypothesis for EFS using a stratified log-rank test (stratified according to randomization stratification factor of age (<60 vs. \geq 60 years)) at the one-sided 2.5% level of significance:

$$H_{01}: \theta_1 \geq 1 \text{ vs. } H_{a1}: \theta_1 < 1$$

Where θ_1 is the hazard ratio (Midostaurin treatment arm vs. placebo arm) of EFS.

In accordance with the stratified randomization scheme used in the study, a stratified two-sided 3-look group sequential log-rank test with a cumulative type I error rate of $\alpha=0.025$, one-sided, will be used to test the null hypothesis (H_{01}). The stratification factor is:

- Age : <60 vs. \geq 60 years

For EFS, the hazard ratio for treatment effect will be estimated and its two-sided 95% confidence intervals will be reported. The estimation will be based on a cox proportional hazards model with treatment and the stratification factor in it.

In addition, survivorship functions will be estimated by using the Kaplan-Meier product-limit method and displayed as graphs. The estimations are performed by treatment group. Median EFS time and its two-sided 95% confidence intervals will be reported for both treatments.

The primary analysis will be based on the FAS. Response status will be based on investigator's assessments as per the International Working Group (IWG) criteria for AML [[Cheson et al 2003](#), [ELN 2017](#)].

7.2.1 Handling of missing values/censoring/discontinuations

In the primary analysis, a patient who had not an EFS event at the date of the analysis cut-off will have his/her EFS censored at the time of the last adequate response assessment before the cut-off date.

Induction failure is defined as failure to achieve CR or CRi with adequate blood count recovery up to 93 days after start of induction phase.

A patient who failed to achieve CR or CRi without adequate blood count recovery in induction phase based on available response assessments, would have his/her EFS event documented at randomization date.

A patient who discontinued induction treatment phase without an efficacy assessment will also be considered to have failed to achieve CR or CRi with adequate blood count recovery and would have his/her EFS event at randomization date as well.

However, a patient who discontinued due to lack of efficacy in the consolidation and post-consolidation treatment phase without any supportive response assessment will be censored at the last adequate response assessment date.

EFS events documented after the initiation of HSCT or new anti-neoplastic therapy will be considered as EFS event for the primary EFS analysis.

If an EFS event is observed after two or more missing or non-adequate response assessments, then EFS will be censored at the last adequate response assessment before the EFS event. If an

EFS event is observed after a single missing or non-adequate response assessment, the actual date of event will be used. An adequate response assessment is considered any disease assessment indicating response status apart from ‘unknown’ or ‘not done’. The event and censoring times for EFS are summarized as follow:

Table 7-1 Primary EFS analysis (event date / outcome)

Situation	Options for event date	Outcome
A No baseline assessment	Randomization date	Censored
B1 Relapse at / or before next scheduled assessment date or death	Date of relapse/death	Event
B2 Relapse/death after exactly one missing assessment	Date of relapse/death	Event
B3 Relapse/death after two or more missing assessments	Date of last adequate assessment	Censored
B4 Relapse/death after HSCT or anti-neoplastic therapy	Date of relapse/death	Event
C Induction failure (incl. lack of post-baseline efficacy assessment)	Randomization date	Event
D No relapse/ no induction failure / no death	Date of last adequate response assessment	Censored
E Treatment discontinuation due to lack of efficacy without documented relapse in the consolidation and post-consolidation treatment phases.	Date of last adequate response assessment	Censored

Of note, a response assessment (especially relapse) can also be done based on one component of response, e.g. peripheral blood.

Missing adequate response assessment is defined as an assessment not done or classified as ‘unknown’. For simplicity, the ‘missing adequate response assessment’ will also be referred as ‘missing assessment’.

As detailed in [Table 7-1](#), the EFS censoring and event date options depend on the presence and the number of missing assessments.

An exact rule to determine whether there are any missing assessments is needed after end of the induction phase. This rule will be based on the distance between the last adequate response assessment date and the event date.

The threshold D1 is defined as the interval between the response assessments plus the protocol-allowed window around the assessments. Similarly, the threshold D2 is defined as 2 times the protocol-specified interval between the response assessments plus the protocol allowed window around the assessments.

During consolidation and post-consolidation treatment phases:

Response assessment are performed **between day 21 and day 28** of each cycle:

- Therefore, for patients with a previous CR or CRi with adequate blood count recovery, the next assessment will be done on the next cycle between day 21 and day 28. The threshold D1 is defined as 28 days (maximum cycle length for patient with CR or CRi

with adequate blood count recovery) + 7 (in case the last assessment was done on day 21) = 35 days and the threshold D2 as 70 days.

- For patients with a previous CRi without adequate blood count recovery, the cycle will be prolonged up to 21 days. Therefore, the threshold D1 is defined as 7 (in case the last assessment was done on day 21) + 21 = 28 days and the threshold D2 is 56 days.

During follow-up phase:

- The threshold D1 is defined as 90 days and the threshold D2 as 2 * 90 days = 180 days

The analysis will assume one missing assessments if the distance between the last adequate response assessment and the event date is within (D1, D2] and 2 or more missing assessment if the distance is larger than D2.

EFS will be summarized between the 2 treatment groups within each of the following subgroups as defined in section 3.8.5. by forest plots

HRs and 2-sided 95% CIs will be provided based on the stratified Cox proportional hazards model. This model will use the BY statement to derive estimates by subgroup. Point estimates of HR and 2-sided 95% CI will be provided by subgroup in a forest plot.

8 Analysis of the key secondary objective: overall survival (OS)

The key secondary objective is to determine if the addition of midostaurin to standard induction and consolidation therapy, followed by single agent post-consolidation therapy improves overall survival (OS) in patients with newly diagnosed FLT3-MN AML.

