10.4.2 Handling of missing values/censoring/discontinuations

In the primary analysis, a patient who had not an EFS event at the date of the analysis cut-off would have his/her EFS censored at the time of the last adequate response assessment before the cut-off date.

A patient who failed to achieve CR or CRi with adequate blood count recovery in induction, would have his/her EFS event due to induction failure documented at the date of randomization.

EFS events documented after the initiation of HSCT or new anti-neoplastic therapy will be considered as EFS event for the primary EFS analysis.

If an EFS event is observed after two or more missing or non-adequate response assessments, then EFS will be censored at the last adequate response assessment before the EFS event. If an EFS event is observed after a single missing or non-adequate response assessment, the actual date of event will be used.

An adequate response assessment is considered any disease assessment indicating response status apart from “unknown” or “not done”.

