bid: twice daily; 1 cycle = 28 days, d: day(s); HSCT: Hematopoietic Stem Cell Transplantation; dauno: daunorubicin; ida: idarubicin; ^aHydroxyurea therapy allowed for ≤ 7 days; ^bMidostaurin/Placebo treatment from day 8 (Induction 1) and from day 4 (induction 2 and consolidation) until 48 hours prior to start of next treatment cycle; ^cAge ≥ 60: no daunorubicin / idarubicin in IND 2, cytarabine 1000mg/m²; ^d Patients in CR/CRi may proceed to HSCT at any time and will enter the post-consolidation after HSCT-recovery; ^e Patients in CRi must have adequate blood count recovery to move to next treatment phase

The study contains three treatment phases:

- Induction treatment phase
- Consolidation treatment phase
- Post-consolidation phase

A patient has to meet the following criteria to continue the next treatment phase:

- A patient achieves CR or CRi **with adequate blood count recovery** defined as the following:
 - Complete Recovery in neutrophil count (≥ 1 x 10⁹/L)
 - Minimal recovery in platelet count (≥ 50 x 10⁹/L)

Of note, a patient not meeting the above criteria up to 93 days after start of induction phase is considered as “*induction failure*”.

The **primary objective** is to determine if the addition of midostaurin to standard induction and consolidation therapy, followed by single agent post-consolidation therapy improves event-free survival (EFS) in patients with newly diagnosed FLT3-MN (SR < 0.05) AML.

The **primary endpoint** is EFS and is determined according to the IWG criteria for AML [Cheson et al 2003, ELN 2017 / Döhner et al 2017] as per investigator assessment. The final analysis was planned to be when a total of 285 EFS events are observed. The first and second interim analyses were planned after observing 40% and 75% of 285 EFS events, respectively.

The **key secondary objective** is to determine if the addition of midostaurin to standard induction and consolidation therapy, followed by single agent post-consolidation therapy improves overall survival (OS) in patients with newly diagnosed FLT3-MN (SR<0.05) AML.

The **key secondary endpoint** is OS. OS was to be initially hierarchically tested if EFS is significant in any of the interim and final analyses following a separate group-sequential plan using Haybittle-Peto stopping boundaries. Since the study was futile at the first interim analysis and therefore stopped due to futility, OS was not tested but will be analyzed and reported in the final clinical study report (CSR).

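### The SAP sentence dating induction-failure EFS events says CRi *without* adequate recovery where the protocol and the SAP's own definitions say *with*: a wording error in the primary-endpoint derivation rule

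*SAP*

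**What the plan says.** SAP 7.2.1 sets the event and censoring dates for EFS. On induction it makes four statements, in this order:

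- A definition: "Induction failure is defined as failure to achieve CR or CRi with adequate blood count recovery up to 93 days" from the start of induction.
- A dating rule: "A patient who failed to achieve CR or CRi without adequate blood count recovery in induction phase", judged on the response assessments available, has the EFS event placed on the randomization date.
- A rule for patients who leave induction with no efficacy assessment: they "will also be considered to have failed to achieve CR or CRi with adequate blood count recovery", and receive the same date.
- A summary in Table 7-1, where row C, "C Induction failure (incl. lack of post-baseline efficacy assessment)", carries the randomization date and the outcome *event*.

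Elsewhere the wording is uniform. SAP 7.1 lists as an EFS component "failure to obtain a CR or CRi with adequate blood count recovery in induction (i.e. induction failure)". SAP section 2 gives the count thresholds for moving to the next phase (neutrophils at least 1 × 10⁹/L, platelets at least 50 × 10⁹/L) and says that "a patient not meeting the above criteria up to 93 days after start of induction phase is considered as" an induction failure. Protocol 10.4.2, which the dating rule carries over, reads "A patient who failed to achieve CR or CRi with adequate blood count recovery in induction". Protocol 7.2.1 classes as a treatment failure a patient whose counts have still not recovered at the end of the prolonged second induction cycle. SAP section 11 states that nothing was changed from the protocol's analysis (the text after that statement is blacked out).

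**The concern.** CRi with and CRi without adequate recovery lie on opposite sides of the line between responder and induction failure. The word that is reversed is the one that draws this line. It also sits in the only running text that dates the event for patients who do have induction response assessments, so it is a sentence a programmer could reasonably code from.

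The stake is the composition of the events placed at time zero for the primary endpoint. These set the initial drop in the Kaplan-Meier curve and feed the hazard ratio, the median and the subgroup forest plots. SAP section 1 also records that the decisions for the final analysis were taken after unblinding. At that stage a primary event rule should have one reading only. Nothing in the documents suggests the reversal was deliberate.

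**Working it through.** **1. The plan's own 93-day limit.** Protocol 7.2.1 builds it from the two induction cycles: 28 + 14 + 1 + 28 + 21 + 1 = 93 days. This reproduces. The 14 and 21 extra days exist to wait for counts to recover, so unrecovered CRi at the end of that wait is exactly the state the limit is meant to classify.

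**2. The same patient under the two texts.** *Recovered* means both count thresholds are met.

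| Induction response by day 93 | Definition plus Table 7-1 row C | Dating sentence, literal and alone |
|---|---|---|
| CR | no event at randomization | no event at randomization |
| Only response is recovered CRi | no event at randomization | **event at randomization** |
| Best response is unrecovered CRi | event at randomization | **no event at randomization** |
| Partial remission or no response | event at randomization | event at randomization |

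The two middle rows disagree, in opposite directions. A patient whose only response is recovered CRi has reached neither CR nor unrecovered CRi, so the literal sentence fails a responder. A patient whose best response is unrecovered CRi has met the literal target, so the literal sentence gives no event.

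**3. What would happen next to the unrecovered-CRi patients.** Protocol Table 7-2 allows relapse only after CR or recovered CRi. Under the literal sentence these patients would therefore have death as their event, or be censored at the last adequate assessment (Table 7-1 row D). Their time-zero events become later events or censored times.

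**4. How many patients.** The documents give no rate for unrecovered CRi. Taking assumed shares of the planned 502:

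- 2%: 0.02 × 502 = 10.0, about 10 patients
- 5%: 0.05 × 502 = 25.1, about 25 patients
- 10%: 0.10 × 502 = 50.2, about 50 patients

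No rate is given for patients whose only response is recovered CRi either, so the opposite error cannot be counted. The study stopped at the first interim analysis, and the number actually randomized is not stated, so 502 is only the planned frame.

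**5. What is not affected.** The 285-event target depends on the hazard ratio, the significance level and the power, not on this wording. Freedman's formula gives (1.960 + 1.2816)² × (1.675/0.325)² = 10.51 × 26.56 = 279.1, rounded up to 280. That is close to the 285 stated for the group-sequential design.

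**The case against.** The strongest reply is that the SAP already answers the question. The definition comes one sentence earlier. The sentence after says *also*, which presupposes that the disputed sentence meant the same thing. Table 7-1, offered as the summary of event and censoring times, dates every induction failure at randomization. The literal reading fails patients who responded, which marks it as a slip of the pen and not a second rule. The sentence can even be parsed loosely as *failed to achieve CR, or reached only CRi without recovery*, which agrees with the definition. Harm arises only if someone programs this one sentence against everything around it, and there is no evidence that anyone did.

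All of that stands, and it sets the limits of the point. A reader might infer that, under this SAP, patients with unrecovered CRi are not induction failures. The documents do not support that: the disputed sentence dates an event, while the preceding sentence defines failure, and with row C it makes these patients failures at randomization.

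A reader might also infer that the slip favours midostaurin, on the argument that an added drug could delay count recovery. The documents do not show this. Protocol 1.2.1.2 and 2.8 report that midostaurin did not lengthen count recovery in the earlier phase III trial, and protocol 2.3 reports no link between exposure and duration of neutropenia. Those data come from FLT3-mutated disease, and that trial dosed for fewer days per cycle. Protocol 1.2.1.1 also describes reduced marrow cellularity in animals. An effect is therefore not excluded, but none is established. Any hazard-ratio shift calculated by removing the unrecovered-CRi events alone would rest on invented rates and would model only half of the literal rule.

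What the reply does not remove is the error itself. The sentence is wrong as written, it belongs to the primary endpoint, and it departs from the protocol without being declared.

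**Conclusion.** The dating sentence in SAP 7.2.1 contains a wording error that reverses protocol 10.4.2 and contradicts the SAP's own definitions. The intended rule is recoverable from the definition and Table 7-1 row C. It should be corrected as a drafting error in a derivation rule.

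The possible consequence is confined to descriptive results. SAP section 7 rules out p-values for the final report, so only the hazard ratio, the median and the Kaplan-Meier curve could move, and only if the program followed the sentence literally. Size and direction cannot be determined from the documents. The figure of about 10 to 50 patients rests entirely on an assumed 2% to 10% of the planned 502.

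Nothing follows about the futility decision. The study was stopped on 23-Sep-2019, while this SAP version is dated 11-Jan-2021, so its wording could not have driven that decision. The version of 02-Sep-2019 is not available for comparison.

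**What to change.** In the dating sentence of SAP 7.2.1, replace *without* by *with*, so that it matches protocol 10.4.2 and the definition one sentence earlier. Record it as a correction of wording, with no change to the planned analysis.

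Then confirm that the EFS program follows the induction-failure definition and Table 7-1 row C for both CRi categories. A short listing would do this: patients whose best induction response is unrecovered CRi, and patients whose only response is recovered CRi, each with EFS date and status. It would also give the actual number of patients concerned.

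The cost is one word in the SAP and one program check.

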7.1.4 Discontinuation of study treatment

Patients may voluntarily discontinue from the study treatment for any reason at any time. If a patient decides to discontinue from the study treatment, the investigator should make a reasonable effort (e.g., telephone, e-mail, letter) to understand the primary reason for this decision and record this information in the patient's chart and on the appropriate CRF pages. They may be considered withdrawn if they state an intention to withdraw, fail to return for visits, or become lost to follow-up for any other reason.

The investigator may discontinue study treatment for a given patient if he/she believes that continuation would be detrimental to the patient's well-being.

Study treatment must be discontinued under the following circumstances:

- Emergence of specific adverse events or laboratory abnormalities under some circumstances outlined in [Section 6.3](#).
- Failure to achieve CR or CRi with adequate blood count recovery in induction or relapse from CR or CRi with adequate blood count recovery.
- Pregnancy (pregnancy will be followed for outcome)
- Any other protocol deviation that results in a significant risk to the patient's safety

The appropriate personnel from the site and Novartis will assess whether study treatment should be discontinued for any patient whose treatment code has been broken inadvertently for any reason.

Patients who discontinue study treatments should NOT be considered withdrawn from the study. They should return for the assessments indicated in [Section 7.2.1](#). If they fail to return for these assessments for unknown reasons, every effort (e.g., telephone, email, and letter) should be made to contact them as specified in [Section 7.1.9](#).

For patients who discontinue treatment for reasons other than documented failure to achieve CR or CRi with adequate blood count recovery in induction phase or relapse from CR or CRi with adequate blood recovery, death, loss to follow-up, or withdrawal of consent, will continue to be followed for efficacy assessment and survival.

The investigator (or designee) must also contact the IRT to register the patient's discontinuation from study treatment.

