8.3.3 Disease Free survival (DFS)

DFS is defined as the time from CR or CRi with adequate blood count recovery to relapse or death due to any cause. Patient who did not relapse nor died will be censored at the last adequate response assessment before cut-off date. DFS will be analyzed for patients who achieved CR or CRi with adequate blood count recovery within 93 days after start of chemotherapy.

Discontinuation due to lack of efficacy or failure to meet continuation criteria (collected on the ‘End of treatment’ and ‘End of post treatment follow up’ disposition pages without supporting documentation of relapse as per IWG criteria for AML [[Cheson et al 2003](#), [ELN 2017](#) / [Döhner et al 2017](#)]) will not be considered relapse for DFS derivation.

DFS will be estimated using the Kaplan-Meier method. The median DFS along with 95% confidence intervals will be presented by treatment group. The stratified Cox regression will be used to estimate the HR of DFS, along with 95% confidence interval.

Table 8-3 Censoring rules for DFS analysis

Situation		Start date	End Date	Outcome
A	Relapse from CR or CRi with adequate blood count recovery or death due to any reason	Date of first occurrence of CR or CRi with adequate blood count recovery	Date of Relapse from CR or CRi with adequate blood count recovery or death due to any reason	Event
B	No Relapse from CR or CRi with adequate blood count recovery nor death due to any reason	Date of first occurrence of CR or CRi with adequate blood count recovery within 93 days after start of treatment	Date of last adequate assessment	Censored

Situation	Start date	End Date	Outcome
C New anticancer therapy given/HSCT prior to relapse from CR or CRi with adequate blood count recovery or death	Date of first occurrence of CR or CRi with adequate blood count recovery	Date of Relapse from CR or CRi with adequate blood count recovery or death due to any reason	Event

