8.3.4 Cumulative Incidence of Relapse (CIR)

Cumulative Incidence of Relapse (CIR) is defined for patients with CR or CRi with adequate blood count recovery within 93 days after start of chemotherapy and is time from achieving the CR or CRi with adequate blood count recovery until the onset of relapse from CR or CRi with adequate blood recovery. Patients without relapse are censored at the last adequate response assessment. Patients who died without relapse are counted as a competing cause of failure.

Table 8-4 Censoring rules for CIR analysis

Situation	Start date	End Date	Outcome
A Relapse from CR or CRi with adequate blood count recovery	Date of first occurrence of CR or CRi with adequate blood count recovery within 93 days after start of treatment	Date of Relapse from CR or CRi with adequate blood count recovery	Event of interest
B Death without relapse	Date of first occurrence of CR or CRi with adequate blood count recovery within 93 days after start of treatment	Death date	Competing event, censored
C No Relapse from CR or CRi with adequate blood count recovery	Date of first occurrence of CR or CRi with adequate blood count recovery within 93 days after start of treatment	Date of last adequate assessment	Censored
D Treatment discontinuation due to 'Lack of efficacy' or 'failure to meet continuation criteria' without documented relapse, i.e. clinical relapse based on investigator claim	Date of first occurrence of CR or CRi with adequate blood count recovery within 93 days after start of treatment	Date of last adequate assessment	Censored
E New anticancer therapy given/HSCT prior to relapse from CR or CRi with adequate blood count recovery	Date of first occurrence of CR or CRi with adequate blood count recovery within 93 days after start of treatment	Date of Relapse from CR or CRi with adequate blood count recovery or death due to any reason	Event of interest

Cumulative Incidence of Relapse (CIR) will be estimated using the Kaplan-Meier method. The median CIR along with 95% confidence intervals will be presented by treatment group. The stratified Cox regression will be used to estimate the HR of CIR, along with 95% confidence interval.

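### SAP Table 7-1 row E censors EFS after a lack-of-efficacy stop with no exception for a later relapse or death, and conflicts with rows B1, B2 and B4

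*SAP*

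**What the plan says.** SAP 7.1 defines EFS as time from randomization to induction failure, relapse from remission, or "death due to any cause, whichever occurs first".

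SAP 7.2.1 opens by censoring patients who have had no EFS event by the cut-off. It then gives a separate rule for lack-of-efficacy stops in consolidation or post-consolidation: such a patient "without any supportive response assessment will be censored at the last adequate response assessment date". Table 7-1 row E restates it as "Treatment discontinuation due to lack of efficacy without documented relapse in the consolidation and post-consolidation treatment phases", with outcome censored at the last adequate response assessment.

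Other rows of Table 7-1 cover deaths:
- Row B1, "Relapse at / or before next scheduled assessment date or death": an event.
- Row B2, relapse or death after exactly one missing assessment: an event.
- Row B3, relapse or death after two or more missing assessments: censored.
- Row B4, relapse or death after HSCT or anti-neoplastic therapy: an event.
- Row D, censoring: limited in its own wording to patients with no relapse, no induction failure and no death.

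Under Protocol 7.1.4, a patient who stops treatment without documented induction failure or relapse "will continue to be followed for efficacy assessment and survival". Protocol 7.1.7 continues these assessments until relapse or death. Protocol 10.4.2, the protocol's EFS censoring section, has no counterpart to row E. SAP section 11 nevertheless reports no change from the protocol analysis.

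For DFS, SAP 8.3.3 says that an undocumented stop of this kind "will not be considered relapse for DFS derivation"; death from any cause remains a DFS event.

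**The concern.** Row D carries a no-death limit and row E does not. A patient who stops under row E and then dies therefore meets two rows of the primary endpoint table with opposite outcomes, and nothing says which one wins. Two programmers following the SAP could derive different EFS data for that patient.

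The direction matters because the reason for censoring is the investigator's view that treatment is failing. Such patients are plausibly closer to relapse or death than those who remain at risk, so censoring them would be informative. If row E prevailed, the Kaplan-Meier curves would be too favorable wherever it applied, and the HR would shift if these stops differed between arms. The same death could also count as a DFS event and an EFS censoring.

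**Working it through.** **1. One patient, all the rules.** Take a patient in CR who stops in post-consolidation for lack of efficacy with no supporting assessment, and who dies more than 35 but no more than 70 days after the last adequate assessment. These limits are the SAP's D1 and D2 for the treatment phases after CR or CRi with adequate recovery. In follow-up they are 90 and 180 days.

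| Rule | Outcome for this death |
|---|---|
| EFS definition, SAP 7.1 | Event |
| Row B2 (treatment-phase limits) or B1 (follow-up limits) | Event at date of death |
| Row B4, if HSCT or new therapy came first | Event at date of death |
| Protocol 10.4.2 | Event; no lack-of-efficacy rule |
| DFS, SAP Table 8-3 row A | Event |
| Row E | Censored at last adequate assessment |

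Row E alone gives a different answer.

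**2. When row E changes anything.** If the patient has no later event, row D already censors at the last adequate assessment. If a death comes more than D2 after that assessment, row B3 censors on the same date, as protocol 10.4.2 requires. Row E therefore alters a result only by overriding an event within D2, or one that row B4 would count.

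**3. Design figures.** To anchor the illustration at the planned effect, use HR 0.675, one-sided alpha 0.025 and 90% power (SAP section 10):
- Schoenfeld: 4(1.960 + 1.282)² / (ln 0.675)² = 273 events.
- Freedman: (1.960 + 1.282)² × (1.675/0.325)² = 280 events.
- Three-look Monte Carlo (114, 214 and 285 events; futility boundary from gamma = −1.2; p < 0.0001 at the second look; z = 1.96 at the end): power 0.901.
- Futility HR: 0.970 at 114 events and 0.910 at 145, against the stated 0.97 and 0.91.

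The planned 285 events for 90% power are reproduced, and this point does not contest them.

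**4. Possible effect on the HR.** The documents give no count of row E patients, so the shares below are assumptions. If a fraction f of events is recoded as censored at random within each arm, then approximately

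observed HR ≈ 0.675 × (1 − f_mid) / (1 − f_pbo).

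For 5% against 2% this is 0.675 × 0.95/0.98 = 0.654. Reversed, it is 0.675 × 0.98/0.95 = 0.696.

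A simulation was run with 2,000 trials per scenario, 502 patients, exponential EFS with control median 12 months, 20 months of uniform accrual, cut-off at 39 months, 5% annual loss, and affected events censored two months early.

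| Events lost, midostaurin / placebo | HR |
|---|---|
| 2% / 2% | 0.675 |
| 5% / 5% | 0.674 |
| 10% / 10% | 0.673 |
| 5% / 2% | 0.656 |
| 2% / 5% | 0.694 |
| 10% / 0% | 0.612 |
| 0% / 10% | 0.743 |

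Only the HR column is informative. The simulated trials averaged 352 events without recoding, more than the planned 285, so power from this run does not apply to the design.

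**The case against.** The strongest reply is that row E means only that the stop is not itself an event. The sentence before it makes stopping induction without an efficacy assessment an event, and the row E sentence follows as a contrast. The opening rule of 7.2.1 censors only patients without an event, rows B1, B2 and B4 keep later deaths, and the DFS section takes the same line. This reading is sensible and may well be what was intended. However, 7.2.1 does not state it, and on this reading row E adds nothing to row D.

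Other parts of the reply stand:
- The scope is narrow. The text requires that no supportive response assessment exists, and relapse can be documented on one component such as peripheral blood.
- The explicit EFS/DFS difference over late deaths comes from row B3. The SAP history shows that censoring after two or more missing assessments was dropped for DFS and CIR. It remains for EFS, in line with protocol 10.4.2.
- Most patients left the study within weeks of the futility stop, so few later events may exist.
- This SAP was finalized after unblinding, so a clarification is safer than a new rule.

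A reader might also carry the fault over to CIR. Table 8-4 row D is already limited to stops "without documented relapse, i.e. clinical relapse based on investigator claim", so a later documented relapse falls under row A of that table. Similarly, row A of Table 7-1 ("No baseline assessment") might look like a parallel case. Eligibility requires a marrow diagnosis, however, and no practical effect can be shown.

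**Conclusion.** The point holds as a conflict within the primary endpoint rules: row E and rows B1, B2 and B4 give opposite outcomes for the same later event, with no precedence stated. Row E taken literally also departs from the EFS definition and from protocol 10.4.2.

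A reader might infer that these events are in fact lost. The documents do not show that; they show that events can be lost, depending on how the table is programmed. Nor do they support an inference that the futility decision was affected. Neither the interim HR nor the number of row E patients is given, and the decision preceded this version of the SAP.

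The size is unknown. Under the assumed losses of 2% to 10%, equal loss barely moves the HR; unequal loss is needed, and none is shown. Investigators were unblinded while some patients continued treatment, so a difference by arm is possible but not documented. Because SAP section 7 rules out p-values in the final report, the consequence is limited to the EFS HR, confidence interval, Kaplan-Meier curves and subgroup forest plots. It is still worth settling before those outputs are derived.

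**What to change.** Replace row E and its sentence in SAP 7.2.1 with:

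> Discontinuation for lack of efficacy without documented relapse is not itself an EFS event; a later documented relapse or death is handled under rows B1-B4; if neither occurs, censor at the last adequate response assessment (row D).

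Referring to all of rows B1 to B4 keeps row B3 in force, so these patients are not exempted from the missing-assessment rule that protocol 10.4.2 applies to everyone.

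Optionally, add the same precedence note to Table 8-4 row D: a later relapse follows row A of that table, and a later death without relapse follows row B.

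The cost is one sentence of SAP text and a check of the derivation code. No new data are needed, since the protocol already collects relapse and survival after treatment stops. Because the SAP postdates unblinding, record the change as a clarification that brings row E into line with the EFS definition and protocol 10.4.2.
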